**Aim 1a Hypothesis:** Abundance of specific SCFA-producing bacterial taxa (e.g. clostridial clusters IV and XIVa) correlates with fecal SCFAs and will distinguish IBS-C from IBS-D and IBS subtypes from controls.

**Aim 1b Hypothesis:** Abundance of specific SCFA-producing bacterial taxa is inversely correlated with fecal inulin and will distinguish IBS-C from IBS-D and IBS subtypes from controls.

**Specific Aim 2:** Determine if GI microbiome signatures in IBS subtypes and controls correlate with fecal BAs or markers of SCFA production (fecal SCFAs or inulin) and test if BAs correlate with fecal SCFAs or inulin.

[figure not shown]
**Aim 1b Hypothesis:** Abundance of BA-dehydroxylating taxa (e.g. genus *Clostridium*) correlates with decreased total fecal BAs in IBS-C and increased total fecal BAs in IBS-D compared to controls.

**Aim 2b Hypothesis:** Abundance of BA-dehydroxylating taxa is associated with fecal SCFAs and fecal inulin.

**Aim 2c Hypothesis:** Fecal inulin and SCFAs differ in IBS-D patients with and without BA malabsorption.

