**Statistical considerations:**

The primary endpoints for analysis will be:

- 1) Total bile acid excretion
- 2) Total and individual fecal excretion of SCFA
- 3) Fecal microbial population
- 4) Fecal inulin

The secondary endpoints for analysis will be:

- 1) Percent primary fecal bile acid excretion
- 2) Stool characteristics (frequency, consistency, ease of passage) based on bowel diary

The associations of fecal SCFAs (continuous variable) with phenotype (using HV as the reference group) and specific microbial taxa will be assessed using a general linear model (GLM) adjusting for relevant covariates. The relative abundance of specific bacterial taxa will be measured and compositional data analysis will be performed to assess the associations of relative microbial taxa abundances with fecal SCFAs or other endpoints (fecal inulin) and to assess whether phenotype alters observed associations. GLM will include specified endpoints, phenotype, the interaction between the endpoint of interest and phenotype, and relevant covariates as prediction variables for SCFAs or other endpoints of interest. False discovery rate (FDR) control will be performed using the Benjamini-Hochberg procedure to correct for multiple testing. We will explore (a) multivariable associations between overall community composition (e.g. Bray-Curtis dissimilarity) with phenotype, fecal SCFAs, or fecal inulin using the PERMANOVA approach adjusting for covariates and (b) the influence of bowel functions on the association between microbial endpoints with fecal SCFAs or inulin in IBS.

Associations of total fecal bile acids with relative abundance of microbial taxa and other specified endpoints (fecal SCFAs or inulin) will be assessed using GLM adjusting for covariates. FDR control will be performed using the Benjamini-Hochberg procedure. Among IBS-D participants, we will test associations between fecal SCFAs or inulin and bile acid phenotype (with or without bile acid malabsorption) using ANCOVA adjusting for covariates. We will explore (a) multivariable associations between overall community composition (Bray-Curtis dissimilarity) with phenotype or total fecal bile acids using the PERMANOVA approach adjusting for covariates and (b) associations between primary fecal bile acids with relative microbial abundances in IBS patients.

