**Sample size and Power:** We will enroll 24 patients with IBS-D, 24 patients with IBS-C, and 24 healthy controls. In order to compensate for withdrawals and loss to follow-up, up to 50 patients could be enrolled to meet the 24 studied in each group.

Sample size assessment is based on results of primary endpoints for Aim 1 from a preliminary dataset acquired by our lab and calculated using ANOVA among three cohort groups. We will have 80% power at the 5% significance level to detect the effect size shown in the table for fecal SCFAs between 19 IBS-C, 19 IBS-D, and 19 HV. Estimated effect sizes for other endpoints of interest are shown in the Table.

Table: Estimated effect sizes

Response (Data show mean+SD)	HV	IBS-C	IBS-D	Effect size (cohen's f)	N per group
Relative abundance of clostridial cluster IV (%)	0.181+0.221	0.392+0.354	2.01+4.06	0.39	22
Relative abundance of clostridial cluster XIVa (%)	0.0814+0.148	0.04+0.0316	0.137+0.31	0.181	99
Relative abundance of genus Clostridium (%)	0.486+0.368	0.84+0.647	2.57+3.85	0.461	16
Overall colonic transit (days)	1.55+0.977	1.52+1.39	1.08+0.649	0.461	65
Total SCFA excretion (µg/mg)	9.94+5.87	16.5+10.1	11.5+2.9	0.235	19

**Inclusion of Women, Minorities, and Children:** Individuals will not be excluded based on gender, race, or ethnicity. Patients with irritable bowel syndrome are comprised of both men and women and have diverse racial and ethnic backgrounds. The prevalence of irritable bowel syndrome among white, blacks, and Hispanics in the U.S. is very similar. Gender and racial/ethnic differences in fecal bile acid and SCFA excretion have not been reported. The communities of Marion County are anticipated to be 65% white, 29% black or African American and 6% other minorities. Children, 18-21 years of age, and adults 21 years or older will be eligible for participation in the study as active participants. However, children below 18 years of age will be excluded.

**Hazardous Procedures, Situations, or Materials and Protection of Human Subjects:** Potential exposure to radiation will be recognized. A Data Safety Monitoring Plan will be proposed. Participant records will have a unique identifier and other identifier information, including name, address, email, home address will be deleted. Only de-identified or anonymized clinical data will be transferred to processing laboratories.

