**Quality assurance/Quality Controls:** Forms will be completed by subjects and reviewed by study staff to ensure completeness. Study coordinator will maintain study records. Study personnel performing stool analysis will be blinded to subject identity.

**Feasibility:** Resources available through our clinical research motility program at Indiana University and through the [name] lab for fecal microbial assessment make completion of this study highly feasible. The PI and her mentors have demonstrated a well-established track record of the techniques to be employed for this proposal in previous studies.

**Internal Validity:** Threats to internal validity include measurement bias, confounding, and chance. We will protect against measurement bias with validated assays and blinding of all study staff when applicable. We will protect against confounding by inclusion of covariates in multivariate analysis. We will control for chance by having sufficient sample size and power as previously calculated.

**External Validity:** Results will reflect the population of Indianapolis, IN and will be generalizable to patients with IBS and similar demographic distribution.

**Strengths and Limitations:** Major strengths of the study include prospective study design, the ability to noninvasively measure transit, assess fecal microbiome, and fecal organic acids. Other strengths include the microbiome expertise of the [name] lab, bile acid expertise of the Mayo Clinic Lab Medicine and Pathology, expertise of the Metabolite Profiling Facility at Purdue University, and expertise of the Complex Carbohydrate Research Center at the University of Georgia. Limitations include cost, potential for participant withdrawal or loss to follow-up and multiple study dates which will be addressed by coordinating schedules to subject's availability and limiting recruitment to the local community.

**Benchmarks:** Primary endpoints will serve as benchmarks for success anticipated to achieve aims. It is anticipated that completion of Aims 1 and 2 will result in 2-3 separate publications, with at least one publication in a high-impact journal. All data will be analyzed and results submitted in abstract form to scientific meetings. Findings from this study will be used to support future grant applications stemming from subsequent research studies investigating novel approaches to restoring the microbiome in IBS and relieving symptoms

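### Sample size rests on a three-group ANOVA; the slopes, interactions and IBS-D ANCOVA that test most of Aims 1 and 2 were never sized, so the general power claim is unsupported

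*Combined protocol and SAP*

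**What the plan says.** **Sizing.** Under Sample size and Power, effect sizes come from a preliminary dataset "acquired by our lab and calculated using ANOVA among three cohort groups". The one explicit power statement is "We will have 80% power at the 5% significance level to detect the effect size shown in the table for fecal SCFAs"; it is made for 19 participants in each of the three groups. The plan itself is larger: "We will enroll 24 patients with IBS-D, 24 patients with IBS-C, and 24 healthy controls". The table gives group means, Cohen's f and N per group for five responses: three taxa, colonic transit and total SCFA.

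**Hypotheses.** The Specific Aims section mixes two kinds. Some are associations, for example "Abundance of specific SCFA-producing bacterial taxa is inversely correlated with fecal inulin", and similar statements link taxa with SCFAs and with bile acids. Others are group contrasts: Aims 1a and 1b also expect taxa to separate the three groups, and Aim 2c compares IBS-D patients with and without bile acid malabsorption.

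**Analysis.** Statistical considerations specifies general linear models with covariates and an interaction with phenotype "to assess whether phenotype alters observed associations", corrected by Benjamini-Hochberg. It also tests SCFAs against phenotype, and uses ANCOVA for Aim 2c.

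**Claim.** Internal Validity concludes: "We will control for chance by having sufficient sample size and power as previously calculated".

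**The concern.** The power calculation and much of the analysis address different quantities. A three-group ANOVA says how well differences in means can be seen. It says nothing about how well a taxon-metabolite slope, or a difference in slopes between phenotypes, can be seen. Nothing under Sample size and Power refers to a slope, a correlation, an interaction, a within-IBS-D contrast or an FDR-adjusted level. Two of the four primary endpoints, total bile acids and fecal inulin, do not appear in the table.

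The Internal Validity sentence nevertheless covers the whole study. What is at stake is the reading of a null result. If a taxon-by-phenotype interaction is non-significant, that sentence would let it be presented as an adequately powered negative, although the chance of detecting a moderate interaction was low.

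**Working it through.** **Inputs from the documents.** 24 per group (72 in total); 5% level; four potential covariates (age, BMI, sex, acid suppression); the table's means, SDs, f and N. The documents give no slope or interaction effect size, so steps 3 and 4 are sensitivity ranges. They assume roughly normal, suitably transformed data. The per-test level of 0.005 is an assumed stand-in for a Benjamini-Hochberg threshold, because the testing family is not defined.

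**1. The plan's own ANOVA figures.** Power is from the noncentral F with 2 and 3n - 3 df and λ = f² × 3n.

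| Response | Printed f | Printed N | N needed by printed f | Power at 24, printed f |
|---|---|---|---|---|
| Cluster IV | 0.39 | 22 | 23 | 83% |
| Cluster XIVa | 0.181 | 99 | 100 | 25% |
| Genus *Clostridium* | 0.461 | 16 | 17 | 94% |
| Colonic transit | 0.461 | 65 | 17 | 94% |
| Total SCFA | 0.235 | 19 | 60 | 40% |

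The three taxon rows reproduce to within one participant; transit and SCFA do not. For cluster XIVa at 24 per group, λ = 0.181² × 72 = 2.36, giving 25%. This taxon is named in Aim 1a.

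**2. The SCFA row.** At f = 0.235, 19 per group gives 32% power, not 80%. From the row's means and SDs with equal groups, the SD of the means is 2.80 and the root-mean-square SD is 6.95, so f = 2.80 / 6.95 = 0.40. That needs 21 per group and gives about 85% at 24. So N = 19 roughly fits the means and SDs but not the printed f. The same rebuild gives f = 0.347 for cluster IV, or 73% at 24. Its claim therefore holds at the printed f only.

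**3. Common taxon slope, n = 72.** Adjusting for phenotype (2 terms) and four covariates leaves 72 - 6 - 3 = 63 for Fisher's z.
- 5%: |r| = tanh[(1.960 + 0.842) / √63] = tanh(0.353) = 0.34.
- 0.005: |r| = tanh[(2.807 + 0.842) / √63] = tanh(0.460) = 0.43.
- Noncentral F (1 and 64 df, λ = 72 f²) needs f² = 0.112 and 0.197. With r = √[f² / (1 + f²)], that is 0.32 and 0.41.

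**4. Taxon-by-phenotype interaction, n = 72.** This has 2 and 62 df (ten model parameters). For within-group correlations r₁, r₂, r₃ and equal group variances, f² = variance of the r's / (1 - mean r²), and λ = 72 f².

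| Pattern | f² | Power at 5%, formula | Power at 5%, simulation |
|---|---|---|---|
| 0 / 0 / 0.3 | 0.02 / 0.97 = 0.021 | 17% | 15 to 16% |
| -0.3 / 0 / +0.3 | 0.06 / 0.94 = 0.064 | 45% | 40% |
| -0.43 / 0 / +0.43 | 0.123 / 0.877 = 0.141 | 80% | about 74% |

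Simulation draws the taxon values at random and fits the full model; the formula is slightly optimistic. At 0.005 the formula gives about 3%, 16% and 48%.

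**5. Aim 2c.** The Significance section puts bile acid malabsorption at up to 50% of IBS-D. With 24 IBS-D patients split 12/12, and 6/18 as an assumed lower share, ANCOVA with four covariates has 80% power only for a standardised difference of about 1.2 to 1.4.

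**The case against.** The strongest defence has three parts.

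**Scope.** The sizing paragraph says that it rests on Aim 1 endpoints and claims 80% power only for SCFAs. It does not claim power for Aim 2, so the missing bile acid row is largely disclosed. This stands for that paragraph. It does not rescue the Internal Validity sentence, which has no such limit, and inulin belongs to Aim 1.

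**Relevance of the ANOVA.** A reader might infer that Aims 1 and 2 are tested only by slopes and interactions, so that the study has no power for its hypotheses. The documents do not support that. The SCFA-by-phenotype test and the group-separation parts of Aims 1a and 1b are contrasts of means, and 24 meets the tabulated N for SCFA, cluster IV and genus *Clostridium*. Large common slopes are also detectable. The power is undemonstrated, not absent.

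**Pilot status.** The opening section calls the work a pilot, and the findings are meant to support later grant applications. Modest power is acceptable in that setting, which lowers the severity. It does not justify asserting adequacy.

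Two further inferences go too far. No passage says that a null interaction will be reported as evidence of no difference; the risk lies in what the wording permits. Nor can a definite loss of SCFA power from the FDR correction be stated, because the testing family is undefined and the SCFA effect size is in conflict.

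**Conclusion.** The concern holds in limited form. The sample size supports three-group comparisons of means at an unadjusted 5%, for responses whose tabulated N is at most 24. It was not calculated for slopes, interactions, Aim 2c, bile acids, inulin or any FDR-adjusted level, and the plan's own table contradicts adequacy for cluster XIVa. The Internal Validity statement is therefore unsupported for most of the stated hypotheses.

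A common slope needs |r| of about 0.32 to 0.34 at 5%, or 0.41 to 0.43 at 0.005. Moderate interactions have roughly 15 to 45% power at 5%, and even -0.43/0/+0.43 falls short of 80% in simulation. These figures rest on 72 evaluable participants, four covariates, near-normal data and assumed effect patterns. Severity: should-fix.

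**What to change.** **Sample size and Power.** Add the detectable common slope and the interaction power at n = 72, both at 5% and at a stated assumed FDR-level threshold. Say that bile acids, inulin, slopes, interactions and Aim 2c were not used for sizing. Reconcile the SCFA row's f and N: the printed 0.235 gives 40% power at 24 per group, whereas about 0.40 from the means and SDs gives about 85%.

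**Internal Validity.** Replace the general sentence by one that limits the power claim to the three-group comparisons of total SCFA, cluster IV and genus *Clostridium*, at their tabulated effect sizes and an unadjusted 5%, with SCFA included only once its row is reconciled. Add that slopes and interactions will be reported with confidence intervals and that non-significance is inconclusive.

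**Cost.** Protocol wording only. The stated power becomes less favourable; no more patients are needed and the analyses do not change.

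### The 80% power for fecal SCFA belongs to the overall three-group test; on the plan's own means and SDs, IBS-D versus HV has about 12–21% at 24 per group

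*Combined protocol and SAP*

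**What the plan says.** Total and individual fecal SCFA excretion is among the primary endpoints.

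- **Sizing (Sample size and Power).** The assessment was "calculated using ANOVA among three cohort groups". The claim is: "We will have 80% power at the 5% significance level to detect the effect size shown in the table for fecal SCFAs". It refers to three groups of 19. The planned size is larger: "We will enroll 24 patients with IBS-D, 24 patients with IBS-C, and 24 healthy controls", with over-enrolment allowed ("up to 50 patients could be enrolled to meet the 24 studied in each group"). The SCFA row of the table gives mean and SD in µg/mg: HV 9.94 (5.87), IBS-C 16.5 (10.1), IBS-D 11.5 (2.9). It prints Cohen's f = 0.235 and 19 per group.
- **Analysis (Statistical considerations).** "The associations of fecal SCFAs (continuous variable) with phenotype (using HV as the reference group) and specific microbial taxa will be assessed" with a general linear model adjusted for covariates, and Benjamini-Hochberg control is applied. The text does not say which phenotype test is the inferential one.
- **Reliance (Internal Validity).** "We will control for chance by having sufficient sample size and power as previously calculated".

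No power is given for any pair of groups.

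**The concern.** An omnibus ANOVA asks whether any of three means differs. A model with HV as reference produces two phenotype coefficients, IBS-C minus HV and IBS-D minus HV. Power for the first question carries over to neither coefficient automatically. Here it carries over very unevenly, because IBS-C lies well above the other two groups and IBS-D lies close to HV.

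IBS-D is one of the two patient groups the study was set up to examine. The Internal Validity section invokes the calculation without limiting it to the overall test. A reader could then take a non-significant IBS-D coefficient as evidence from an adequately powered comparison, which it would not be.

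**Working it through.** **Inputs.** Means, SDs, f, 19 and 24 per group are from Sample size and Power. Two-sided 5% is assumed for the contrasts, because sidedness is not stated. Everything is unadjusted and before FDR control.

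**1. The plan's own figure.** For three equal groups of n, the power is that of a noncentral F with 2 and 3n − 3 df and noncentrality 3n·f².

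- Printed f = 0.235: power is 32% at 19 per group, and 80% needs 60 per group.
- f from the row itself: the grand mean is (9.94 + 16.5 + 11.5)/3 = 12.65. The SD of the three means (divisor 3) is 2.80. The pooled SD is √[(5.87² + 10.1² + 2.9²)/3] = 6.95. So f = 2.80/6.95 = 0.403, which gives 76% at 19 per group and 86% at 24. Reaching 80% needs 21 per group.
- 80% at exactly 19 per group corresponds to f of about 0.425.

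So 19 per group roughly fits the row's means and SDs, but not the printed f. Neither reproduces 80% exactly.

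**2. Where the omnibus effect comes from.** The sum of squares of the three means about the grand mean is 23.49. The part due to IBS-C against the average of the other two groups (10.72) is (16.5 − 10.72)²/1.5 = 22.27, or 95%. The part due to IBS-D against HV is 1.56²/2 = 1.22, or 5%. If IBS-D and HV are both set to 10.72, omnibus power at 24 per group falls only from 86% to 84%.

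**3. Contrasts.** Power is from the noncentral t with noncentrality (Δ/SD)·√(n/2). Three variance treatments are shown: the three-group SD of 6.95 with 3n − 3 df, the SD of the two groups compared with 2n − 2 df, and Welch.

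| Contrast | Δ (µg/mg) | Two-group SD | n = 19: three-group / two-group / Welch | n = 24: three-group / two-group / Welch |
|---|---|---|---|---|
| IBS-C vs HV | 6.56 | 8.26 | 82% / 66% / 66% | 90% / 77% / 76% |
| IBS-D vs HV | 1.56 | 4.63 | 10% / 17% / 17% | 12% / 21% / 21% |
| IBS-C vs IBS-D | 5.00 | 7.43 | 59% / 52% / 51% | 69% / 63% / 61% |

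For IBS-D vs HV at 24 per group, the noncentrality is (1.56/6.95)·√12 = 0.78 with the three-group SD and (1.56/4.63)·√12 = 1.17 with the two-group SD. The powers are 12.0% and 20.8%, so the shortfall from 80% is 59.2 to 68.0 points.

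**4. What 24 per group can detect.** With 80% power, the detectable difference from HV for IBS-D is about 3.8 µg/mg (SD 4.63) to 5.7 µg/mg (SD 6.95), against 1.56 in the preliminary data. By the normal approximation n = 2(1.96 + 0.84)²(SD/Δ)², 80% power at 1.56 would need about 139 (SD 4.63) to 312 (SD 6.95) per group.

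**The case against.** The strongest reply is that reference coding is only a parameterisation. The same model yields a 2-df phenotype test, which is the test an ANOVA calculation sizes, and the power section promises nothing for individual pairs. This stands: a reader might infer that the plan commits to separate tests of each subtype against HV, and the documents do not say so. But they do not name the 2-df test either, and the HV-referenced coefficients will be in the output.

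A reader might also cite Aim 1a ("correlates with fecal SCFAs and will distinguish IBS-C from IBS-D and IBS subtypes from controls") as requiring SCFA contrasts between the groups. It does not, because its subject is the abundance of bacterial taxa. The point rests only on the phenotype model for SCFA.

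The planned model also contains taxa, covariates and interactions, so its phenotype coefficients are not raw mean differences. That is fair. The contrast powers here are unadjusted benchmarks on the same footing as the plan's own ANOVA. Covariates could move them either way, and FDR control would tend to lower them.

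Finally, the study calls itself a pilot, the sizes of the preliminary groups are not given, and nothing presents 1.56 µg/mg as a target difference. This argues against asking for more participants. It does not support an unqualified statement that power is sufficient. Nor do the documents say that a null IBS-D result would be reported as no difference; that is a risk of misreading, not a stated intention.

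**Conclusion.** The point holds in a limited form. The 80% describes the overall three-group test only, and it does not apply to IBS-D vs HV. If the preliminary difference of 1.56 µg/mg is real, a non-significant IBS-D vs HV result at 24 per group is likely, at about 79–88%. It is not close to certain: on the more favourable variance assumption about one study in five would reach significance.

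The weakness is specific to that contrast. IBS-C vs HV is reasonably powered at 24 per group, and IBS-C vs IBS-D lies in between. A reader might conclude that the study is too small for SCFA overall. The table's means and SDs do not support that, since they give the overall test about 86% at 24 per group.

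The figures assume normal data, equal groups, two-sided 5%, no covariates and no FDR adjustment. They take the preliminary means and SDs at face value. The SDs run from 2.9 to 10.1, so ranges are the honest summary. The mismatch between the printed f and its own row is a separate defect. The contrast powers do not use that f.

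**What to change.** - **Sample size and Power:** state SCFA power as omnibus power only, using the value the row's means and SDs give at the planned 24 per group (about 86%; 76% at 19). Reconcile the printed f of 0.235, which gives 32% at 19 per group, with the row's own f of about 0.40. Add the contrast powers at 24 per group as ranges: about 76–90% for IBS-C vs HV, 12–21% for IBS-D vs HV and 61–69% for IBS-C vs IBS-D. Note that they are unadjusted and before FDR control.
- **Statistical considerations:** name the 2-df phenotype test as the confirmatory test of SCFA by phenotype, matching the sizing. Report the HV-referenced contrasts as estimates with 95% confidence intervals.
- **Internal Validity:** limit the sentence on sufficient power to the overall test.

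The cost is a few sentences, with no additional participants, data or change in sample size. The downside is a less favourable power statement for IBS-D.

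### The plan's only power statement contradicts its own table: f = 0.235 with 19 per group gives 32% power, not 80%, and the printed f is probably the wrong entry

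*Combined protocol and SAP*

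**What the plan says.** The protocol's Sample size and Power paragraph bases the calculation on a preliminary dataset, "calculated using ANOVA among three cohort groups". It makes one power claim: "We will have 80% power at the 5% significance level to detect the effect size shown in the table for fecal SCFAs". The group size behind that claim is 19 in each of the three cohorts. The planned size is larger: "We will enroll 24 patients with IBS-D, 24 patients with IBS-C, and 24 healthy controls".

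The table of estimated effect sizes gives means and SDs by group, Cohen's f and N per group for five responses. The row "Total SCFA excretion" shows f = 0.235 and N = 19. The colonic transit row shows f = 0.461 and N = 65. The genus Clostridium row also shows f = 0.461, with N = 16.

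SCFA is a primary endpoint in Statistical considerations: "Total and individual fecal excretion of SCFA". The Internal Validity paragraph relies on the calculation: "We will control for chance by having sufficient sample size and power as previously calculated".

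**The concern.** The power sentence takes its effect size from the table, so the sentence and the table cell have to agree. The table looks wrong before any calculation. The Clostridium and transit rows have the same f but N of 16 and 65, and one test at one alpha and one power cannot give both. The SCFA effect (0.235) is smaller than the cluster IV effect (0.39), yet it is said to need fewer participants (19 against 22).

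This is the only power justification in the plan, and it concerns a primary endpoint. Read literally, the study has about a one-in-three chance of detecting the stated SCFA effect at 19 per group. If the f cell is the misprint, the design may be sound but its justification cannot be checked. Anyone who reuses the printed f to size a later study would get a wrong answer.

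**Working it through.** **Inputs.** Three groups of equal size, alpha 0.05, target power 80%, and the f, N, means and SDs in the table. All come from Sample size and Power.

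**Formula.** One-way ANOVA with k = 3: df1 = 2, df2 = 3n − 3, noncentrality λ = 3n·f². Power is the probability that a noncentral F(df1, df2, λ) exceeds the 5% critical value of the central F.

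**Step 1: each row at its printed f and N.**

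| Row | f | N | Power at printed f and N | n for 80% at printed f | f for 80% at printed N |
|---|---|---|---|---|---|
| Cluster IV | 0.39 | 22 | 79.7% | 23 | 0.391 |
| Cluster XIVa | 0.181 | 99 | 80.0% | 100 | 0.181 |
| Clostridium | 0.461 | 16 | 79.6% | 17 | 0.463 |
| Transit | 0.461 | 65 | >99.9% | 17 | 0.224 |
| SCFA | 0.235 | 19 | 31.9% | 60 | 0.423 |

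For SCFA, λ = 3 × 19 × 0.235² = 3.15 and the critical value of F(2, 54) is 3.17. The first three rows reproduce to within one participant per group, which is rounding. SCFA is short by 60 − 19 = 41 per group.

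**Step 2: other readings.** With power of 70%, 80% or 90% and alpha of 0.05 or 0.10, f = 0.235 needs between 37 and 78 per group. A two-group ANOVA needs 73, reading 0.235 as a standardised difference needs 285, and reading it as f² needs 15. None gives 19. For f = 0.461 the corresponding three-group range is 11 to 21, a two-group ANOVA needs 20, and a standardised difference needs 74. None gives 65. Exchanging the two f values does not repair the rows exactly either: 0.235 needs 60, not 65, and 0.461 needs 17, not 19.

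**Step 3: f from the printed means and SDs, equal pilot groups.** f = SD of the three means (divisor 3) ÷ root-mean-square SD.

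- SCFA: means 9.94, 16.5, 11.5 have SD 2.798. Root-mean-square SD = √[(5.87² + 10.1² + 2.9²)/3] = 6.949. f = 0.403.
- Transit: 0.215 / 1.050 gives f = 0.205.

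Both are near the values implied by the N column (0.423 and 0.224) and far from those printed (0.235 and 0.461). Equal groups do not reproduce the three sound rows, however (0.347, 0.200 and 0.402 against 0.39, 0.181 and 0.461), so 0.403 is not offered as the true value. The pilot groups were probably unequal.

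**Step 4: unequal pilot groups.** The document gives no pilot sizes. I assume that one set applies to every row and let each group range from 4 to 40.

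- Sets that put all three sound rows within 0.01 of their printed f give SCFA f of 0.391 to 0.439 and transit f of 0.182 to 0.243, with f = √(SSB/SSW). With the pooled SD instead, the ranges are 0.388 to 0.406 and 0.164 to 0.200.
- Over all sets, with no fit required, transit f stays below 0.29, so 0.461 cannot come from that row.
- SCFA f comes down to 0.235 only near HV 4, IBS-C 40, IBS-D 4. If no group is more than four times another, it is 0.31 to 0.46.

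One illustrative set is HV 16, IBS-C 6, IBS-D 9 with √(SSB/SSW). For SCFA the weighted mean is 11.66, SSB = 188.1, SSW = 15 × 5.87² + 5 × 10.1² + 8 × 2.9² = 1094.2, and f = √(188.1/1094.2) = 0.415. Its f values for the five rows, in the order of Step 1, are 0.390, 0.181, 0.458, 0.224 and 0.415. These need 23, 100, 17, 66 and 20 per group, each one more than printed, as in the sound rows of Step 1. The N column can therefore be right throughout. This is one set that fits, not evidence of what the pilot sizes were.

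**Step 5: power at the planned 24 per group.** The smallest f with 80% power is 0.374. SCFA power is 39.8% at f = 0.235, 85.9% at 0.403 and 89.2% at 0.423.

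**The case against.** The strongest reply is that little follows from the error. If the f cells are misprints, N = 19 stands, the plan enrols 24 per group, and SCFA power is about 86% to 89%. The study also describes itself as a pilot. That stands as a limit on severity: the 32% and 40% figures apply only if 0.235 is the true target.

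The transit row carries little weight in itself. Transit is not a listed endpoint or main variable, the visit procedures include no transit measurement, and its N of 65 is not a recruitment target. The row serves here mainly as supporting evidence of a copying error, because its f repeats the Clostridium value.

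Which cells are wrong is also an inference, resting on undisclosed pilot sizes assumed common to all rows. That is fair. The mismatch between f and N is certain; the attribution to the f cells is probable. Since the table was read from a PDF, the two cells should first be checked against the original page. All rows have complete cells and three are coherent, however, so nothing suggests an extraction fault.

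None of this removes the contradiction. The plan makes a specific 80% claim, and its own table does not support it.

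**Conclusion.** The point holds. As printed, f = 0.235 with 19 per group gives 31.9% power and not 80%, and f = 0.461 does not go with 65 per group. These results need only the three-group ANOVA, the 5% level and the printed figures.

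The two f cells are probably the wrong entries, with the true SCFA value near 0.4. That part assumes that the printed means and SDs are right and that one set of pilot sizes underlies every row. No true power shortfall is shown. The correct f cannot be recovered from the document, because the pilot group sizes are missing. The point should be fixed, but it is an error in the justification and not a demonstrated flaw in the design.

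**What to change.** 1. Check the SCFA and transit f cells against the source calculation, recompute f (and N if needed) from the pilot data, and correct the table.
2. State the pilot group sizes and the formula used for f.
3. Restate the power sentence so that f, N and power agree, preferably at the planned size. For example: With 24 per group, a three-group ANOVA at the 5% level has 80% power for f of at least 0.374; the pilot SCFA effect of f = [recomputed value] gives [x]% power. Here x is about 86 if f is about 0.40, and about 40 if 0.235 is confirmed.
4. Point the Internal Validity paragraph to the corrected figure.

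The cost is two table cells, one sentence and the pilot sizes. Enrolment, endpoints and analyses do not change. If 0.235 is confirmed, the plan should say openly that power for that effect is about 40% at 24 per group.
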